### 11.1.7 Expectedness

The expectedness of an AE or SAR shall be determined according to the specified reference document containing safety information (e.g., most current product label). Any AE that is not identified in nature, severity, or specificity in the current study drug reference document(s) is considered unexpected. Events that are mentioned in the product label as occurring with a class of drugs or as anticipated from the pharmacological properties of the drug, but not specifically mentioned as occurring with the particular drug under investigation are considered unexpected.

## 11.2 Suspected Unexpected Serious Adverse Reaction

AEs that meet the criteria of serious, related to study drug, and unexpected per investigator brochure, qualify for expedited reporting to the regulatory authorities. The sponsor or their designee will notify the FDA and all participating investigators in a written IND safety report of an SAR that is serious and is unexpected, as determined by the sponsor. The reporting will occur as soon as possible, but not later than 15 calendar days after sponsor determines that it qualifies for expedited reporting. The sponsor will identify all safety reports concerning a similar SAR, and will analyze the significance of the SAR in light of the previous, similar reports. Follow-up reports will be sent to investigators to inform and update them about an important suspected adverse reaction if it significantly affects the care of the participants or conduct of the study.

### 11.2.1 Day Zero

Day zero (0) is the calendar day that the sponsor is first notified of an event. Day zero can also be the date the event qualified for expedited reporting as determined by the sponsor.

### 11.2.2 Pregnancy

Pregnancy occurring during a clinical investigation, although not considered a serious adverse event, must be reported to DCRI within the same timelines as a serious adverse event. The pregnancy will be recorded on the appropriate paper pregnancy tracking form. The pregnancy will be followed until final outcome. Any associated AEs or SAEs that occur to the mother or

fetus will be recorded in the AE/SAE eCRF, within the study database.

### **11.3 Recording and Reporting of Adverse Events**

The Site Investigator is responsible for monitoring the safety of participants enrolled into the study at the study sites. Non-serious AEs that occur from the time of informed consent and up to 7 days post last product use will be collected in the study database. These events should be documented in the source documents and followed until clinically resolved.

SAEs, except for those anticipated AEs listed above, occurring from *signed informed consent* to the 7 days post last product use will be captured on the SAE form. Unless exempted as described above, all SAEs, whether or not deemed drug-related or expected, must be reported to the sponsor (or designee) by the investigator or qualified designee within 24 hours of first becoming aware of the event. The investigator or qualified designee will enter the required information regarding the SAE into the appropriate module of the study database, which will automatically result in distribution of the information to the sponsor or their designee (e.g. DCRI Safety Surveillance). If the study database system is temporarily unavailable, the event, including the investigator-determined causality to study drug should be reported via the back-up paper SAE form to the sponsor or their designee. Upon return of the availability of the electronic data capture (EDC) system, the SAE information must be entered into the study database.

### **11.4 Follow-up**

When additional relevant information becomes available, the Investigator will record follow-up information according to the same process used for reporting the initial event as described above. The Investigator will follow all reportable events until resolution, stabilization or the event is otherwise explained.

The sponsor or their designee will follow all SAEs until resolution, stabilization, until otherwise explained or until the subject completes the final follow-up, whichever occurs first.

Investigators are also responsible for promptly reporting AEs and SAEs to their reviewing IRB/EC in accordance with local requirements.

The DSMB will review detailed safety data approximately every 6 months throughout the study.

### **11.5 Anticipated Disease Related Adverse Events**

The following AEs are anticipated, disease-related events in patients admitted with AHF:

- **Arrhythmias:** This refers to both atrial and ventricular arrhythmias.
- **Sudden Cardiac Death:** This refers to witnessed cardiac arrests and sudden deaths without an otherwise apparent cause such as trauma or malignancy.

- **Acute Coronary Syndrome:** This refers to unstable angina, non ST segment elevation myocardial infarction (NSTEMI), and ST segment elevation myocardial (STEMI).
- **Cerebrovascular Event:** This refers to cerebrovascular accidents (stroke) of any cause (hemorrhagic, ischemic, or embolic) and transient ischemic attack (TIA).
- **Venous Thromboembolism:** This includes both deep venous thrombosis and pulmonary embolus.
- **Lightheadedness, Presyncope, or Syncope:** This includes dizziness, lightheadedness, or fainting from any cause.
- **Acute kidney injury as defined by KDOQI guidelines:** Acute kidney injury, typically defined as a rise in creatinine > 0.3 mg/dL over 48 hours, or progressive loss of renal function over time.
- **Worsening HF:** Worsening of symptoms and signs of heart failure requiring intensification of IV therapy or initiation of mechanical therapy.
- **Hypokalemia** ( $K^+$  <3.5 mmol/L)
- **Hypomagnesemia** (Mg <1.0 mEq/L or <0.70 mmol/L)

All anticipated disease related events, will not be captured as AEs/SAEs during the study, but will be entered on the appropriate eCRF module.

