### 11.1.6 Assessment of Causal Relationship

A medically-qualified investigator must assess the relationship of any AE to the use of study drug, based on available information, using the following guidelines:

- **Not related:** There is not a reasonable causal relationship to the investigational product and the adverse event.
- **Unlikely related:** No temporal association or the cause of the event has been identified, or the drug or biologic cannot be implicated.
- **Possibly related:** There is reasonable evidence to suggest a causal relationship between the drug and adverse event.
- **Related:** There is evidence to suggest a causal relationship, and the influence of other factors is unlikely.

The Investigator reports causality, but the sponsor retains the final decision on causality when filing to the FDA.

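### The anticipated-event exemption makes no exception for serious listed events suspected to be treatment-related, so these have no stated 24-hour route to the sponsor

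*Combined protocol and SAP*

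**What the plan says.** Section 11.5 opens its list with "The following AEs are anticipated, disease-related events in patients admitted with AHF". The ten classes are arrhythmias, sudden cardiac death, acute coronary syndrome, cerebrovascular event, venous thromboembolism, lightheadedness to syncope, acute kidney injury, worsening heart failure, hypokalemia and hypomagnesemia. Of sudden cardiac death it says: "This refers to witnessed cardiac arrests and sudden deaths without an otherwise apparent cause such as trauma or malignancy". Stroke and syncope are included whatever their cause. The section ends: "All anticipated disease related events, will not be captured as AEs/SAEs during the study, but will be entered on the appropriate eCRF module".

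Section 11.3 describes what goes on the SAE form as "SAEs, except for those anticipated AEs listed above", and sets the reporting duty with "Unless exempted as described above, all SAEs, whether or not deemed drug-related or expected, must be reported to the sponsor", within 24 hours of awareness. The list is actually in 11.5, below, but the closing sentence of 11.5 creates the exemption in any case.

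Two other sections bear on the same events. Section 11.1.6: "A medically-qualified investigator must assess the relationship of any AE to the use of study drug". Section 11.2: "AEs that meet the criteria of serious, related to study drug, and unexpected per investigator brochure, qualify for expedited reporting" to the regulators, no later than 15 calendar days after the sponsor's determination.

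**The concern.** Exempting common disease events from SAE reporting is a normal way to limit noise in an acute heart failure trial. It usually stops where the investigator suspects the treatment. Here no such limit is written, and the 24-hour duty, which otherwise applies whether or not an event is thought drug-related, gives way to the exemption.

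Safety is part of the primary objective (4.1). Section 11.6 calls experience with subcutaneous furosemide limited, and outpatient subjects infuse themselves at home (8.2). If a subject has a stroke, a ventricular arrhythmia or a sudden death during home use and the investigator suspects the infusion, the sponsor needs to know quickly, because 11.2 leaves the expedited-reporting decision to the sponsor. The pilot also informs whether the main study of about 300 patients proceeds as designed (2.0, 5.2).

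**Working it through.** There is no figure to reproduce. The pilot is descriptive, and the point rests on reading the reporting sections against each other.

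1. **Is there an exception for suspected-related events?** Sections 11.1.3, 11.1.6, 11.1.7, 11.2, 11.3, 11.4, 11.5, 12.2, 12.3 and 13.1 contain none. By contrast, 11.2.2 puts pregnancy on SAE timelines although it is not classed as an SAE. The protocol does restore a clock expressly where it wants one.

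2. **Are the listed classes purely disease events?** Six of the ten match effects that 11.6.1 and 11.6.2 attribute to furosemide:
   - arrhythmia (11.6.1, as a sign of fluid or electrolyte imbalance)
   - venous thromboembolism (thrombosis and embolism in 11.6.1)
   - hypokalemia (11.6.1)
   - hypomagnesemia (11.6.1)
   - acute kidney injury (kidney damage in 11.6.1)
   - lightheadedness (dizziness and orthostatic hypotension in 11.6.2)

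3. **Is causality still assessed?** Section 11.1.6 covers any AE and states no exemption, and 11.5 itself calls the listed events AEs. The duty is therefore not expressly waived. But 11.5 then declines to capture the events as AEs or SAEs, and 11.3 mentions causality only in connection with SAE reporting. For a listed event, no form, field or deadline is stated.

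4. **Can the sponsor apply 11.2?** An event must be serious, related and unexpected. Under 11.2.1, day zero is the day the sponsor is first notified or the date on which the sponsor determines that the event qualifies. Both need the sponsor to have the information. Sudden death is not named in 11.6, and 11.1.7 treats an event anticipated only from pharmacology as unexpected, so a related sudden death would probably qualify. That cannot be confirmed: the reference document is not in the file, and 11.1.7 gives the product label as its example where 11.2 names the investigator brochure.

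5. **Does another route fill the gap?**

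| Route | Section | What is stated |
|---|---|---|
| Anticipated-event eCRF module | 11.5 | No deadline; automatic distribution to the sponsor is described only for SAE entry (11.3) |
| Death and hospitalization event forms | 12.3 | Listed as components that may be included; no clock, no causality field |
| Outpatient calls on D1, D3, D5 and D14 | 10.2.2, 10.2.5 | Inform the site; no timed duty to tell the sponsor |
| IRB reporting | 11.4 | Covers AEs and SAEs; reach over events not captured as such is unclear; not a report to the sponsor |
| DSMB review | 12.2; 11.4 and 13.1 | At completion of the pilot; about every 6 months |

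None gives the sponsor timed notice of a listed event.

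6. **Scale.** One subject is 1/20 = 5% of a phase, or 1/40 = 2.5% of the pilot. This shows only how much weight one event carries. It is not a probability, and the documents give no rate from which to derive one.

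**The case against.** The best defence is that the exemption covers disease-related events, and sudden cardiac death is defined by the lack of another apparent cause. A death that the investigator attributes to the infusion arguably has such a cause and falls outside the list. That reading is available for sudden death, and it means the text is ambiguous there. It does not help for stroke or syncope, which are listed whatever their cause.

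Other limits stand. Serious events not on the list, such as anaphylaxis or serious device injury, remain under the 24-hour rule. Hypokalemia, hypomagnesemia and lightheadedness are often non-serious and then never carried a 24-hour duty, so the count of ten overstates the practical reach. The eCRF module and any separate safety plan are not in the file and may already hold a relatedness field or an alert.

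A reader might also infer more than the text supports:
- **That no causality assessment is needed.** Section 11.1.6 requires one for any AE. What is missing is where and when to record and send it.
- **That 11.2 would apply to any related sudden death, and that 11.5 forbids reporting it.** Section 11.2 also requires the event to be unexpected, and it contains no exemption. The sponsor's duty stands; the weakness is in the flow of information.
- **That the SAE route is the only fast signal.** It is the only stated timed route to the sponsor. Site calls and IRB reporting exist beside it.

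**Conclusion.** The point holds as a gap in the reporting rules. A serious listed event suspected to be related to the drug or pump has no stated 24-hour route to the sponsor, and its causality assessment has no stated destination or deadline. The exemption covers ten classes, six of which overlap with the protocol's own furosemide risks. For these events the sponsor's notice goes from 24 hours to no stated limit.

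This rests on the protocol text alone. It assumes that no safety plan or eCRF specification outside the file supplies the missing route. Whether a given event would then need expedited reporting depends on the reference document.

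The documents do not support going further and treating every fatal or life-threatening listed event as wrongly exempted. Exempting expected disease events is a deliberate choice, and removing all fatal ones whatever the cause would nearly empty the sudden-death class. The sponsor should still say what it intends for them. The change should be made: it is specific, bears on subject safety and costs little.

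**What to change.** Reconcile 11.1.6, 11.2, 11.3 and 11.5 as follows.

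- Add to 11.3 and 11.5: *The exemption does not apply to a listed event that meets the SAE definition and that the investigator considers at least possibly related to the study drug or the pump. Such an event is entered on the SAE form within 24 hours of awareness, with a causality assessment.* The pump needs naming because 11.1.6 refers only to study drug.
- Make sure the anticipated-event eCRF module records relatedness.
- State whether fatal listed events judged unrelated also keep 24-hour reporting.
- While these sections are open, correct the cross-reference in 11.3 to the list in 11.5, and name one expectedness reference in 11.1.7 and 11.2.

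The cost is protocol wording, one eCRF field if it is not already there, and some additional SAE forms among 40 subjects. No dose, schedule or clinical rule changes.

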## 11.6 Summary of the Risks

Experience with subcutaneous furosemide injection has been limited. Although preclinical studies did not suggest any local irritation or reaction from administration of the study drug, local discomfort or irritation following administration of the study drug cannot be excluded.

The subcutaneous administration of furosemide is expected to be associated with the same systemic adverse experience profile as the intravenous and intramuscular administration. The systemic adverse experience profile for intravenous and intramuscular furosemide is listed below.

### 11.6.1 Drug Adverse Reactions

#### General

Excessive diuresis may cause dehydration and blood volume reduction with circulatory collapse and possibly vascular thrombosis and embolism, particularly in elderly patients. As with any effective diuretic, electrolyte depletion may occur during furosemide therapy, especially in patients receiving higher doses and a restricted salt intake. Hypokalemia may develop with furosemide, especially with brisk diuresis, inadequate oral electrolyte intake, when cirrhosis is present, or during concomitant use of corticosteroids, ACTH, licorice in large amounts, or prolonged use of laxatives may exaggerate metabolic effects of hypokalemia, especially myocardial effects.

All patients receiving furosemide therapy should be observed for these signs or symptoms of fluid or electrolyte imbalance (hyponatremia, hypochloremic alkalosis, hypokalemia, hypomagnesemia, or hypocalcemia): dryness of mouth, thirst, weakness, lethargy, drowsiness, restlessness, muscle pains or cramps, muscular fatigue, hypotension, oliguria, tachycardia, arrhythmia, or gastrointestinal disturbances such as nausea and vomiting. Increases in blood glucose and alterations in glucose tolerance tests (with abnormalities of the fasting and 2-hour postprandial sugar) have been observed, and rarely, precipitation of diabetes mellitus has been reported. In patients with severe symptoms of urinary retention (because of bladder emptying

disorders, prostatic hyperplasia, urethral narrowing), the administration of furosemide can cause acute urinary retention related to increased production and retention of urine. Thus, these patients require careful monitoring, especially during the initial stages of treatment. In patients at high risk for radiocontrast nephropathy, furosemide can lead to a higher incidence of deterioration in renal function after receiving radiocontrast compared to high-risk patients who received only intravenous hydration prior to receiving radiocontrast. In patients with hypoproteinemia (e.g., associated with nephrotic syndrome) the effect of furosemide may be weakened and its ototoxicity potentiated. Asymptomatic hyperuricemia can occur and gout may rarely be precipitated. Patients allergic to sulfonamides may also be allergic to furosemide. The possibility exists of exacerbation or activation of systemic lupus erythematosus. As with many other drugs, patients should be observed regularly for the possible occurrence of blood dyscrasias, liver or kidney damage, or other idiosyncratic reactions.

### **11.6.2 Information for Patients**

Patients receiving furosemide should be advised that they may experience symptoms from excessive fluid and/or electrolyte losses. The postural hypotension that sometimes occurs can usually be managed by getting up slowly. Potassium supplements and/or dietary measures may be needed to control or avoid hypokalemia.

Patients with diabetes mellitus should be told that furosemide may increase blood glucose levels and thereby affect urine glucose tests. The skin of some patients may be more sensitive to the effects of sunlight while taking furosemide.

Hypertensive patients should avoid medications that may increase blood pressure, including over-the-counter products for appetite suppression and cold symptoms.

### **Adverse Reactions**

Adverse reactions are categorized below by organ system and listed by decreasing severity.

#### **Gastrointestinal System Reactions**

(1) Hepatic encephalopathy in patients with hepatocellular insufficiency (2) Pancreatitis (3) jaundice (intrahepatic cholestatic jaundice) (4) increased liver enzymes (5) anorexia (6) oral and gastric irritation (7) cramping (8) diarrhea (9) constipation (10) nausea (11) vomiting.

#### **Systemic Hypersensitivity Reactions**

(1) Severe anaphylactic or anaphylactoid reactions (e.g., with shock) (2) Systemic vasculitis (3) interstitial nephritis (4) necrotizing angiitis.

#### **Central Nervous System Reactions**

(1) Tinnitus and hearing loss (2) paresthesias (3) vertigo (4) dizziness (5) headache (6) blurred vision (7) xanthopsia.

#### **Hematologic Reactions**

(1) Aplastic anemia (2) thrombocytopenia (3) agranulocytosis (4) hemolytic anemia (5) leukopenia (6) anemia (7) eosinophilia.

#### **Dermatologic-Hypersensitivity Reactions**

(1) Exfoliative dermatitis (2) bullous pemphigoid (3) erythema multiforme (4) purpura (5) photosensitivity (6) urticaria (7) rash (8) pruritus (9) Stevens-Johnson Syndrome (10) toxic epidermal necrolysis.

### Cardiovascular Reaction

(1) Orthostatic hypotension may occur and be aggravated by alcohol, barbiturates or narcotics, (2) Increase in cholesterol and triglyceride serum levels.

### Other Reactions

(1) Hyperglycemia (2) glycosuria (3) hyperuricemia (4) muscle spasm (5) weakness (6) restlessness (7) urinary bladder spasm (8) thrombophlebitis (9) transient injection site pain (10) fever.

## 11.6.3 Device Adverse Reactions

### SC2Wear System

Mild skin irritation such as redness, itching and edema or skin trauma and abrasion may occur during exposure or removal of the adhesive. Removal of the device may be uncomfortable or painful. Rarely, allergic reactions to the adhesive may occur. If the subject knows they are sensitive or allergic to medical adhesive tape, they should not participate in the study.

The needle used to inject the drug into the subcutaneous tissue is automatically inserted at the beginning of the infusion cycle, and automatically retracted at the end. The needle is 27 gauge and 8.5 mm. Common risks with needle injection include pain or discomfort upon needle injection, or minor bruising from needle movement. Injection site reactions were minimal and limited to very slight edema and very slight to definite erythema. An accidental needle stick injury may occur if (a) the needle appears before the Pump is placed on the body or (b) the Pump falls off the body while it is pumping. If either of the above happens, the Pump should be handled carefully.

As with all devices that use medical adhesives for adherence the usual risks are: it is possible that there may be instances of complete or near complete dislodgement of the device from the abdominal skin. In a previous study designed to look at adhesive effectiveness in combination with the sc2Wear device, 2 out of 132 device applications (1.5%) became completely detached from the skin. In the same study 6 subjects (4.5%) had evidence of medical adhesive-related skin injury (MARSI). The finding of rare cases of dislodgement and rare cases of MARSI indicate that the objective to find an adhesive with the optimal balance between adhesive strength and skin tolerability has been achieved. Using more aggressive adhesive would increase the risk of MARSI which carries a risk of infection and may reduce the patient acceptance of this treatment. Should dislodgement occur, there would be minimal risk to the patient, as it would be obvious and clearly discoverable by the patient being treated. In such instances, the patients will be instructed to call their healthcare provider. In this study, patients are instructed to contact the study team in case of complete dislodgement or if leakage is detected.

## 12.0 STATISTICAL CONSIDERATIONS AND DATA MANAGEMENT PROCEDURES

### 12.1 Overview

There will be no formal hypothesis tested, and statistical analysis will be descriptive in nature.

## **12.2 Analysis of Safety Data and Statistical Monitoring Plan**

Interim data analysis for efficacy and futility will not be conducted due to relatively small size and short duration of this clinical trial. Safety data will be assessed at the completion of the pilot study by the NHLBI-appointed DSMB. The safety analyses will be based on the entire ITT population. Safety will be evaluated by comparing the rates of occurrence and severity of AEs of the study population to expected rates of occurrences.

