## **5.0 BASIC STUDY DESIGN**

SUBQ-HF Pilot is a multicenter clinical trial of selected AHF patients with persistent congestion after initial stabilization. Broadly speaking, the pilot phase is designed to evaluate the overall safety and feasibility of a strategy based on subcutaneous delivery of furosemide. The pilot phase will consist of an inpatient and outpatient pilot occurring as described below and will be followed by review of data by the HF Network Steering Committee and Data Safety Monitoring Board. The same inclusion and exclusion criteria will be used for both phases of the pilot.

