# **13 STUDY ADMINISTRATION**

## **13.1 Data and Safety Monitoring Board (DSMB)**

A DSMB has been appointed by the NHLBI for the HFN. This committee consists of a group of highly experienced individuals with extensive pertinent expertise in HF and clinical trials. The DSMB will advise the HFN Steering Committee regarding the continuing safety of current participants and those yet to be recruited, as well as the continuing validity and scientific merit of the trial. Safety data, summarized at the treatment level, will be assessed approximately every 6 months by the DSMB. The safety analyses will be based on the entire ITT population. During the evaluation phase, safety will be evaluated by comparing the occurrence of AEs and changes in laboratory values between study strategies.

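### Section 12.2 judges pilot safety by AE rates and severity, but 11.5 keeps ten anticipated event types out of AE capture and Section 12 does not say that they are counted

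*Combined protocol and SAP*

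**What the plan says.** Section 12.1 says only that the analysis is descriptive. Section 12.2 then gives the pilot's safety evaluation: "Safety will be evaluated by comparing the rates of occurrence and severity of AEs of the study population to expected rates of occurrences". It supplies no expected rates and no source for them.

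Section 11.5 lists ten event types as anticipated in acute heart failure: arrhythmia; sudden cardiac death; acute coronary syndrome; cerebrovascular event; venous thromboembolism; lightheadedness, presyncope or syncope; acute kidney injury (AKI); worsening heart failure; hypokalemia; and hypomagnesemia. It closes: "All anticipated disease related events, will not be captured as AEs/SAEs during the study, but will be entered on the appropriate eCRF module". Section 11.3 carries the exemption into serious-event reporting, where the SAE form takes "SAEs, except for those anticipated AEs listed above". For non-serious events 11.3 states no exemption of its own, so theirs comes from 11.5 alone.

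Laboratory change is named as a safety measure once, in 13.1: "During the evaluation phase, safety will be evaluated by comparing the occurrence of AEs and changes in laboratory values between study strategies". The Executive Summary places that phase in a separate protocol.

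Oversight is described in general terms. Under 5.0 the pilot "will be followed by review of data by the HF Network Steering Committee and Data Safety Monitoring Board". Under 5.2 both bodies review the results, and the main study goes ahead unchanged unless they raise real safety or feasibility concerns. Sections 11.4 and 13.1 give the DSMB safety data about twice a year, and 12.2 gives it safety data at the end of the pilot. None of these sections lists what the data comprise.

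**The concern.** Safety is half of the primary objective (4.1), and the pilot's result feeds the decision in 5.2 on a trial of about 300 evaluable patients. The harms most to be expected from parenteral furosemide self-administered at home include electrolyte depletion, renal injury and symptoms of volume depletion. Several of these are on the 11.5 list. If the AE rate in 12.2 is programmed from the AE and SAE forms, it leaves them out. Neither 11.5 nor 11.3 limits the exemption by severity or causality.

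Two further consequences follow. The severity scale in 11.1.5 is written for AEs, and nothing says that module events are graded, so the severity part of 12.2 may not reach them. And if the source of the expected rates counts such events as AEs, the pilot's rate would be set against a benchmark with a wider numerator and would look low for that reason alone.

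**Working it through.** The plan gives no figure to reproduce: 20 subjects per phase is stated without a calculation, and no event rate is given. The check is therefore a side-by-side reading, followed by arithmetic on assumed rates.

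**1. Overlap between the exempt list and the stated drug risks**

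| 11.5 event | Where 11.6 names it | Strength of the link |
|---|---|---|
| Hypokalemia | 11.6.1, General | Direct |
| Hypomagnesemia | 11.6.1, General, among imbalances to watch for | Direct |
| Venous thromboembolism | 11.6.1, General: "Excessive diuresis may cause dehydration and blood volume reduction with circulatory collapse and possibly vascular thrombosis and embolism, particularly in elderly patients" | Direct, though given as a possibility |
| Lightheadedness/syncope | 11.6.2, Central Nervous System Reactions: "3) vertigo (4) dizziness (5) headache" | Direct for dizziness |
| Arrhythmia | 11.6.1, General | Looser: listed as a sign of imbalance |
| AKI | 11.6.1, General: "patients should be observed regularly for the possible occurrence of blood dyscrasias, liver or kidney damage, or other idiosyncratic reactions" | Looser: a generic caution |

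Six of the ten appear in some form, four of them fairly directly.

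**2. Two readings of 11.5**

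- *Literal.* Exempt events are not AEs for the study. The 12.2 numerator is then subjects with an event on the AE or SAE form.
- *Data-entry rule.* The events remain AEs but are keyed on another form. The 12.2 numerator should then include the module, but Section 12 mentions neither the module nor its tabulation.

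Two programmers could each follow the text and produce different AE tables.

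**3. What the choice of reading does to the rate**

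Let m be the number of subjects in a phase whose only events are 11.5 events. Then

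rate counting both sources − literal AE rate = m/20,

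which is 5 percentage points per such subject, whatever else is observed.

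If the true per-subject rate of any 11.5 event is p (assumed), the expected number affected is 20p and P(at least one) = 1 − (1 − p)^20.

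| p (assumed) | Expected of 20 | P(at least one) |
|---|---|---|
| 5% | 1 | 64.2% |
| 10% | 2 | 87.8% |
| 20% | 4 | 98.8% |
| 30% | 6 | 99.9% |

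The number affected is an upper limit for m, because some of these subjects may also have another AE.

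The extreme case has no other AE at all. The literal result is then 0/20 (exact 95% CI 0% to 16.8%). Counting the module gives 3/20 = 15% (3.2% to 37.9%) if m = 3, or 6/20 = 30% (11.9% to 54.3%) if m = 6.

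A more realistic case has 8/20 (40%) with any event. If 25%, 50% or 75% of those eight have only 11.5 events, the literal rate is 6/20 = 30%, 4/20 = 20% or 2/20 = 10%.

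**4. Whether the data exist to close the gap**

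The module holds the events. Appendix A lists creatinine, BUN, sodium, potassium and magnesium as protocol values, at D0 to D2 for inpatients and at D0, D2 (+2 days) and D7 (+2 days) for outpatients. There are two complications:

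- Sections 8.1 and 10.1.1 make the inpatient D1 and D2 values standard of care only, so they may be incomplete.
- The main AKI criterion in 11.5 is a creatinine rise above 0.3 mg/dL over 48 hours. An inpatient D0 to D2 pair can meet it. An outpatient D2 sample may be drawn as late as day 4, so the D0 to D2 interval can run well past 48 hours, and D2 to D7 is nominally five days.

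**The case against.** The best counter-argument is that 11.5 is a form-routing rule. Its title and opening line call these events AEs, and they meet the AE definition in 11.1.1. Anticipated disease events are also the natural ones to have expected rates. This is a reasonable reading and may be what was intended. It removes the claim that the events are certainly excluded, but it does not supply the missing statement that they are counted.

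A reader might infer that these harms go unseen. The documents do not support that. The events are entered in the database, and the DSMB and Steering Committee receive safety data and results in general terms, so they would probably see them.

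A reader might also infer that serious drug-related cases escape all reporting. Section 11.2 states no 11.5 exemption from expedited reporting of serious, related, unexpected events.

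Nor would the AE table be empty of diuretic and device harm. Dehydration, hypotension, hyponatremia, injection-site pain and skin reactions are not on the 11.5 list and remain AEs. Hospitalizations, ED visits and unscheduled visits are collected separately.

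Finally, 13.1 does not show that pilot laboratory values will go unanalysed. Its sentence concerns a comparison between strategies, which a single-arm pilot cannot make. On pilot laboratory values the plan is simply silent.

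It is also fair that Section 12 is short throughout and names no table for weight, symptoms or device problems. Brevity suits a descriptive pilot. Here, though, the text states a numerator, and another section restricts it. That is more than missing detail.

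**Conclusion.** The point stands in a limited form. Section 12.2 rests the pilot's safety evaluation on AE rates and severity, while 11.5 (and 11.3 for SAEs) takes ten event types out of AE capture. Literally read, the specified rate omits several foreseeable effects of the drug. Read as data entry, 11.5 allows them to be counted, but Section 12 does not commit to it. This is an ambiguity in the analysis plan and not a failure to collect data. It should be corrected because the result feeds the decision in 5.2.

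The size cannot be derived from the documents. The only fixed quantity is 5 percentage points per affected subject in a phase of 20. The 5% to 30% event rates, the 8/20 and the shares of subjects with only 11.5 events are all assumptions, and the 0/20 case requires that no other AE occurs. A low bias against expected rates is conditional on a benchmark that the plan does not identify. Confidence is moderate, because the routing reading is plausible and general review would probably bring the events to light.

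**What to change.** Add to 12.2:

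*For each phase, the number and percentage of subjects (exact 95% CI) with (a) an AE, (b) each 11.5 event type from its eCRF module, and (c) either, will be tabulated, by severity where recorded. AKI will be counted by the 11.5 definition, including a creatinine rise >0.3 mg/dL between measurements no more than 48 hours apart; changes over longer intervals will be shown as laboratory changes. Creatinine, BUN, sodium, potassium and magnesium will be summarised as change from D0 and worst value, with n per time point. These tables will go to the DSMB and Steering Committee before the decision in 5.2, and any comparison with expected rates will use the same event definitions.*

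The AKI sentence keeps the 48-hour criterion where sampling allows it, without treating a slower outpatient change as a 48-hour rise. Reporting n per time point handles inpatient laboratory values that were not drawn.

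The cost is one paragraph and a few descriptive tables, with no new visits, samples or patients. The tables will be uncontrolled, so they cannot separate drug effect from the course of heart failure. Inpatient laboratory summaries may be incomplete, and the reported event rate will look less favourable than one from the AE forms alone.
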